## 1. Summary:

**Introduction:** Hyperkalemia is a serum Potassium (K) level of more than 5.5 mEq/L. It is a common emergency medicine presentation and can be life-threatening. Because of the emergency in correcting hyperkalemia, different medications are used to reduce high potassium levels to normal as soon as possible. Salbutamol inhalers, Glucose solutions, and Insulin are the main medications for managing hyperkalemia. Insulin and Dextrose shift potassium ions into body cells by stimulating the sodium/potassium ATP pump. Its effect starts in less than fifteen minutes and can last up to sixty minutes. It usually reduces potassium up to 1.1 mEq/l. There are different recommendations for Insulin dose and rate of administration for patients with hyperkalemia.

**Method:** This will be a multi-center, prospective, double-blind, non-inferiority, randomized control trial. 336 hyperkalemia patients will be randomized to the intervention group 5 units of intravenous Regular insulin and 10 units of intravenous insulin groups with fifty ml of Dextrose Fifty percent. They will be enrolled once their potassium level is 5.5mEq/L or more. The attending physician/ investigator and patient will be blinded about the dose of insulin that the patient received. Serum potassium will be measured at 0 and at 120 minutes from the start of the medications. Random blood glucose will be measured at 0, 60, and 120 minutes by Glucometer. The safety of our patients will be assessed by documentation of all adverse events, vital signs, and clinical assessment before and after drug administration. The study will end at 2 hours from insulin administration.

**Aim:** Our research idea aims to compare two recommended doses of Insulin (5 Units vs. 10 Units of Regular insulin given intravenously over thirty minutes) in the management of patients with hyperkalemia.

**Primary objective:** Mean reduction in serum potassium level using the main laboratory results at two hours from medication administration.

**Secondary objectives:** effect of initial (baseline) potassium level on the mean potassium reduction, and frequency of hypoglycemia between the 2 groups. Does the initial (baseline) blood glucose level will affect the function of insulin/dextrose in lowering potassium levels?

**Patient Population:** Adult patients (Aged 18 years and older) who present to the Emergency department at Sultan Qaboos University and Royal Hospital for evaluation and are found to have potassium levels of 5.5 mEq/L and above.

**Intervention:** Single dose of 5 units of intravenous insulin over 30 minutes with 50 ml of Dextrose 50%.

**Clinical Measurement:** Mean reduction of potassium level using the main laboratory results at 2 hours from insulin/dextrose administration. We will follow serum potassium by blood sampling. Hypoglycemia will be followed by a bedside glucometer.

**Outcome:** reduction of potassium level at 2 hours from medication administration and medication safety.

## 2. Introduction: literature review and justification of the study.

Hyperkalaemia is the most dangerous and deadly electrolyte imbalance seen in all health institutions (1). Potassium is mainly an intracellular cation. The normal level of potassium is between 3.5 to 5.5 mEq/L (12). It is critical to identify and manage hyperkalemia as soon as possible. Hyperkalaemia can affect multiple systems including the central and peripheral nervous system, gastrointestinal system, renal system, and neuromuscular system including the cardiac muscles (2) The most dangerous effect of hyperkalemia is cardiac toxicity. Hyperkalaemia affects the heart by depressing its electrical and muscular functions leading to cardiac arrhythmia and sudden cardiac death (1).

Potassium plasma level is determined by three main factors: the amount of potassium intake, the distribution of plasma between the extracellular fluid and the cells, and potassium excretion with urine (3).

There are different medications used for the treatment of hyperkalemia. The known regimen has 3 components (1) (4). The 1st group of treatment is cardiac muscle-stabilizing agents like Calcium gluconate (1) (4). The 2nd group is the medications that shift Potassium from the plasma to inside the cells like Insulin and Salbutamol (1) (4). The 3rd group of treatments is the ones that eliminate potassium from the body like dialysis and diuretics (1) (4). The standard dose of insulin is 10 units of Regular insulin as a bolus with dextrose 50% 50 to 100 ml (1) (4) (5). Some guidelines recommend an insulin dose between 5-10 units of Regular insulin as a bolus (2).

There are multiple studies done to monitor the efficacy and safety of potassium-lowering agents like insulin and other medications. A recent retrospective cohort study showed no difference between 5 Units and 10 units in lowering potassium levels (6).

Most of the studies done to compare insulin doses were retrospective studies and most of them were done on a patient with renal insufficiency (acute and chronic). These studies showed no difference in the efficacy of lowering potassium levels between 5 units of insulin and 10 units of insulin. They showed 5 units of insulin have the advantage of fewer hypoglycemia events compared to 10 units. As Bairbre A. McNicholas et al 2017, Heather A LaRue 2017, and Kayvan Moussavi 2021 (7) (8) (9) (10) showed the same finding

Ziv Harel and Kamel S. Kamel 2016 in their systemic review of articles that looked into the different doses of insulin found no difference in the efficacy of lowering potassium between 10, 12, and 20 units of insulin (11)

Kayvan Moussavi et al 2020 in their observation study showed that less than 10 units of insulin cause less incidence of hypoglycemia but the amount of potassium reduction was less in patients who received less than 10 units (8). But this study was a retrospective for patients who attended the emergency department in a single center. Although they mentioned less than 10 units have less efficacy but the doses of less than 10 units range from 3 units to 8 units as it will be difficult to conclude this range of values. (8).

### The gap in the studies:

From these studies our question came. If 5 units of intravenous regular insulin reduce potassium level as effective as 10 units of insulin with less hypoglycemia why we do not use

it as our standard dose to avoid a possible complications and will be less cost as half the dose of insulin will be used in the future as standard.

Most of the studies were retrospective studies and a lot of confounders may affect the result, that's why this study will add much to the argument in regarding to the best dose in managing patient with hyperkalemia. Also the investigators will review the rate of hypoglycemia and who is more at risk to avoid this complication among those patients. In our secondary objective the investigators will analyse the effect of blood sugar level and potassium level in patient response to treatment.

### **3. Objectives and hypothesis of the study:**

#### **Primary outcome:**

1. To study the efficacy of two intravenous insulin doses (5 units and 10 units) in reducing serum potassium level in patients receiving hyperkalemia treatment using the main laboratory measurements. (the aim of reduction of 0.6 mmol/l +/- 0.2 mmol/L) (1). Blood sample will be collected and send to the main laboratory for analysis at two hours from medications administration. The efficacy of the 2 doses will be measured at 2 hours from administration of medications by comparing the amount of changes in potassium level at two hours.

#### **Secondary outcome**

1. Study the mean difference of the response to the anti-hyperkalemic measures based on the level of initial potassium (serum potassium before given any medications – At baseline) (the investigators will categorize potassium level into groups mild (5.5–6 mmol/l), moderate (6–6.5 mmol/l) and severe (>6.5 mmol/l) and will see the mean difference in reduction in potassium level in between the 2 doses).
2. Association of mean potassium reduction with initial blood sugar level (blood sugar level before given any medications – At Baseline) on potassium reduction (the investigators will categorize blood sugar into groups: Below 10mmol/L, 10.1-14.9 mmol/L, and 15 – 19.9mmol/L among each group the investigators will see the mean potassium reduction level).
3. Incidence of hypoglycemia (random blood sugar (RBS)  $\leq$  3.89 mmol/l in Diabetic patients and less than 3 mmol/l in non-Diabetic patients) (12). (and risk factor Characteristic of patients of higher risk of developing hypoglycemia (the investigators will investigate which group of patients will have a high risk of hypoglycemia ((e.g: initial Glucose level, initial creatinin/renal function, comorbidities, type of dialysis...)).

## Study hypothesis

No difference between 5 and 10 units of intravenous regular insulin in lowering potassium levels in patients with hyperkalemia at 2 hours.

## 4. Feasibility of the study

As hyperkalemia is very common our investigators can find a good number of cases. Also, it will be a multicentre study with the inclusion of emergency department patients in the study. The American College of Emergency Physicians (ACEP) recommends the use of both 5 units and 10 units of insulin as treatment of hyperkalemia published on their anti-hyperkalemia protocol in 2021 (13). With an average of 1 patient per day, the research team can achieve the target sample size within the timeline. Funding will be requested from the research council (Ministry of Higher Education, Research and Innovation) and Sultan Qaboos University fund.

## 5. Research Design and Methods

### Study design

Prospective double blinded, randomized controlled clinical trial, in adults (from age 18) who presents to the emergency department (ED) at Sultan Qaboos University Hospital, and Royal Hospital, with hyperkalemia (potassium level  $>5.5$  mEq/l, Written consent will be obtained from the patient. Eligible subjects will be enrolled (Appendix: [Written informed consent](#)).

### Characteristics of study area and target population

This study will be conducted in 2 different hospitals, Sultan Qaboos University Hospital and Royal Hospitals both are tertiary hospitals in Muscat region. The research team might extend to other hospitals if noticed that we are short on patient number. Patient will be selected based on the potassium level in the main laboratory report. When potassium level  $\geq 5.5$  mEq/l the patient will be screened for inclusion and exclusion criteria. Our 5.5 mEq/l lab cut off came from Ministry of health protocol (see appendix: [Ministry of health hyperkalemia management protocol](#)) and ACEP protocol for hyperkalemia management (13).

### Control Group

The patient will receive 10 U of regular insulin + Dextrose 50% over 30 minutes + salbutamol nebulization 10mg in 3ml normal saline over 15min, calcium gluconate will be given according to the physician responsible about the case.

### Intervention Group

The patient will receive 5 U of regular insulin + Dextrose 50% over 30 minutes + salbutamol nebulization 10mg in 3ml normal saline over 15min, calcium gluconate will be given according to the physician responsible about the case.

## Primary and secondary endpoints

### Primary endpoint:

- Mean reduction in serum potassium level at 2 hours from insulin administration. Blood sample from the patient will be obtained for potassium measurement. The samples will be sent to the main laboratory for potassium level analysis.

### Secondary endpoint:

- Mean difference of the response to the antihyperkalemic measures based of the baseline level of potassium.
- Incidence of hypoglycemia and risk factors characteristic of patients of higher risk of developing hypoglycemia.
- Association of mean potassium reduction with baseline blood sugar level.

## Selection and withdrawal of subjects:

### Inclusion and exclusion criteria

#### Inclusion criteria:

- Hyperkalemia patients with lab potassium levels equal to or more than 5.5 mEq/L ( $\geq 5.5$  mEq/L)\*.
- Adult: aged 18 years or more.
- Agreed to participate in the study.

\* If a doctor/Investigator decided to start anti-hyperkalemia medications based on the VBG/ABG patient can be enrolled but if the main laboratory value is less than 5.5 mEq/L patients will be excluded

#### Exclusion criteria:

- Cardiac arrest
- Hyperglycemia with random blood sugar 20 mmol/L (13) or with acute diabetic complications like Diabetic Ketoacidosis / Hyperosmolar Hyperglycemic State.
- Hypoglycemia with random blood sugar (RBS)  $\leq 3.89$  mmol/l in Diabetic patients and less than 3 mmol/l in non-Diabetic patients.
- Allergies for any medication in the protocol.
- Pregnancy.
- Hemolyzed potassium level as reported by the main lab.
- Hemolysis, Tumor lysis syndrome, or Rhabdomyolysis due to the ongoing release of potassium.
- Acidosis with a pH less than 7.1 will require Sodium bicarbonate (NaHCO3).
- A patient who will need urgent Furosemide (Lasix), and or dialysis during the study period of 2 hours.
- Refused to participate.

### Withdrawal criteria

A subject/patient may be withdrawn from the study at any time for any reason and without penalty or prejudice. The following situations may be cause for a subject to be withdrawn from the study:

- Subject did not fulfil the inclusion or exclusion criteria.

- Subject experienced a significant complication, deemed due to the study treatment.
- Subject developed an inter-current illness, condition, or procedural complication that would interfere with continued participation.
- Subject voluntarily withdrew consent.
- Subject was in violation of the protocol.
- Treating Physician decided it is in the best medical interest of the subject to terminate involvement.

Upon occurrence of a serious adverse event or intolerable adverse event, the principal investigator will be notified. If a subject is discontinued from study treatment due to a serious adverse event, the event will be followed until resolution. The investigational staff must fill the withdrawal form (Appendix: [Withdrawal form](#)).

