## **7. Study flow**

The study protocol will be for a total of 2 hours. All groups will follow the same path except the dose of insulin administered. After the result of potassium level ( $\geq 5.5$  mEq/L) patient will be screened for inclusion and exclusion criteria at the same time all other medications except insulin can be administered as the doses are fixed. Eligible patient will have to sign a

written consent if they agreed to be involved in our study. The initial data and basic labs will be collected before starting the study protocol. The incharge doctor/investigator will take the random code and write it on the data collection sheet of that patient from already prepared list/code and give the assigned nurse the medications administration card/form (see appendix: [medications administration form](#)).

Every patient will receive:

- Potassium lowering agent:
    - Intravenous Regular insulin 5 units **OR** 10 units with Glucose 50% water 50 ml over 30 minutes according to the randomization.
    - Salbutamol nebulization 10 mg in 3ml normal saline over 15 minutes.
  - The physician will decide the need of cardiac stabilizing agents (e.g Calcium Gluconate) as indicated by the physician in-charge of the patient.
- Please see [study flow chart](#) in the attachment.

5 Units insulin group	10 units insulin group
Medications to be administered: • IV Insulin Regular 5 units with Dextrose 50 % 50 ml over 30 minutes. • Salbutamol 10 mg NEB over 15 minutes.	Medications to be administered: • IV Insulin Regular 10 units with Dextrose 50 % 50 ml over 30 minutes. • Salbutamol 10 mg NEB over 15 minutes.

Figure 1: Treatment. RBS: Random Blood sugar. IV: Intravenous. NEB: Nebulization.

Initial investigations will include:

ECG, Urea and electrolytes, Creatinine, eGFR, Random blood sugar, complete blood count, Magnesium level, bone profile, phosphate level, will be attached if not sent before.

Repeated labs will be with these frequencies:

**Potassium** level: 0 and 120 minutes from medications administration time.

**Blood sugar**: 0, 60 and 120 minutes from medications administration time.

The study will be over at 2 hours (120 minutes) or by patient decision to withdraw from the study.

	0	Post involvement	
		60	120
Timeline (minutes) from medications administration	0	60	120
Eligibility screen	*		
Consent	*		
Randomization	*		
Basic labs: ECG, U&E, RBS, CBC, Mg, bone profile, PO4, VBG.	*		
Study Medication administration	* →		

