## 21. Criteria for terminating the study.

A subject/Patient who is enrolled in the study and for whom study treatment is prematurely terminated will be discontinued from study treatment. After discontinuation/early release from the study, the subject/patient will receive standard-of-care treatment as per the treating clinician. End of Study Efficacy and Safety assessments will be performed, if appropriate and whenever possible.

The study will be terminated when 336 subjects are enrolled, and all data is obtained and documented on the data collection sheet and transferred to Epi-Data program.

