Secondary outcomes

1. Study the mean difference of the response to the anti-hyperkalemic measures based on the level of initial potassium (serum potassium before given any medications – At baseline) (the investigators will categorize potassium level into groups mild (5.5–6 mmol/l), moderate (6–6.5 mmol/l) and severe (>6.5 mmol/l) and will see the mean difference in reduction in potassium level in between the 2 doses).
2. Association of mean potassium reduction with initial blood sugar level (blood sugar level before given any medications – At Baseline) on potassium reduction (the investigators will categorize blood sugar into groups: Below 10mmol/L, 10.1-14.9 mmol/L, and 15 – 19.9mmol/L among each group the investigators will see the mean potassium reduction level).
3. Incidence of hypoglycemia (random blood sugar (RBS) \leq 3.89 mmol/l in Diabetic patients and less than 3 mmol/l in non-Diabetic patients) (12). (and risk factor Characteristic of patients of higher risk of developing hypoglycemia (the investigators will investigate which group of patients will have a high risk of hypoglycemia ((e.g: initial Glucose level, initial creatinin/renal function, comorbidities, type of dialysis...)).

Safety outcomes

Adverse events are reported at each visit.

Populations

Intention-to-treat (ITT)

All randomized study subjects. This will be seen as the primary population for the analysis.

Per Protocol (PP)

All randomized study subjects completing the whole study period (complete cases). For a specific analysis, study subjects with missing data on any of the variables in the model will be excluded from the analysis. Analyses of this population is seen as a sensitivity analysis to investigate whether conclusions are sensitive to assumptions regarding the pattern of missing data.

Statistical analysis

Primary outcome

The data analysis for the clinical trial will be conducted using IBM SPSS Statistics version 29.0. Categorized variables will be presented as percentages, and continuous variables will be presented as means with standard deviations or medians with interquartile ranges. The primary outcome, the reduction in serum potassium levels, will be analyzed using a linear mixed effect model that adjusts for baseline potassium levels. A p-value of <0.05 will be considered statistically significant.

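### Patients can be withdrawn for a treatment complication or protocol violation without a required 120-minute sample, so the only post-treatment potassium value can be lost for dose-related reasons

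*Protocol*

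**What the plan says.** **Withdrawal (Protocol Section 5, Withdrawal criteria).** The opening rule is broad: "A subject/patient may be withdrawn from the study at any time for any reason and without penalty or prejudice". The situations that may lead to withdrawal include "Subject experienced a significant complication, deemed due to the study treatment", "Subject was in violation of the protocol", and a treating physician's judgement that leaving is in the patient's interest. For serious adverse events the section adds: "If a subject is discontinued from study treatment due to a serious adverse event, the event will be followed until resolution". It does not mention the 120-minute potassium.

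**After withdrawal (Protocol Section 21).** For patients discontinued or released early: "End of Study Efficacy and Safety assessments will be performed, if appropriate and whenever possible".

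**End of study (Protocol Section 7).** "The study will be over at 2 hours (120 minutes) or by patient decision to withdraw from the study". Withdrawal by staff is not listed here. The potassium schedule is "level: 0 and 120 minutes from medications administration time", so there is one value after baseline. Glucose is taken at 0, 60 and 120 minutes.

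**Analysis sets (SAP).** Populations defines ITT as "All randomized study subjects. This will be seen as the primary population for the analysis", and per protocol as complete cases. Statistical analysis restricts ITT to subjects with one or more usable values after baseline, and per protocol to those who completed as planned with all values present. Non-inferiority requires both analyses to agree. No imputation or other handling of withdrawn patients is given.

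**The concern.** The treatment is a single infusion and follow-up lasts two hours. Ending a patient's participation in that window can cost the one measurement on which the trial is decided.

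One of the grounds, a complication attributed to treatment, may depend on the randomised dose. The Protocol's introduction cites studies with fewer hypoglycaemic events on 5 units than on 10. If patients with complications leave more often from one arm, and their potassium response differs from that of the other patients, the remaining groups are no longer the randomised groups.

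Requiring both ITT and per protocol to agree does not protect against this. A patient without a 120-minute potassium is absent from both.

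**Working it through.** **1. What happens to one patient.** Take a patient who is randomised, has a complication before 120 minutes, and is withdrawn.
- Section 5 permits the withdrawal.
- Section 21 does not firmly require the 120-minute sample.
- Section 7 provides no other potassium value after baseline.
- The SAP model adjusts for baseline potassium. With no value after baseline the patient adds nothing to the treatment contrast, mixed model or not.
- The patient belongs to ITT under Populations, is not in the potassium analysis under Statistical analysis, and is not in per protocol under either definition.

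**2. The plan's own allowance for loss.** 320 × 1.05 = 336, so 336 − 320 = 16 patients for losses of every kind. This step reproduces. The 320 itself does not follow from its stated inputs: 2 × (1.960 + 1.282)² × 0.62² / 0.2² gives 202 per arm, or 404. That is a separate matter and nothing below depends on it.

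**3. Size of the possible bias.** The documents give no withdrawal rate and no link between complications and potassium response, so these inputs are assumptions. Let *h* be the share of an arm with a complication by 60 minutes, *w* the share of those withdrawn without a 120-minute sample, and *x* their extra fall in potassium (mmol/L) relative to the rest of the arm.

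Understatement of an arm's mean fall = *hx* − *h*(1 − *w*)*x* / (1 − *hw*)

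The shift in the comparison is the 10-unit value minus the 5-unit value.

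| | Moderate case | High case |
|---|---|---|
| *h*, 10 vs 5 units | 0.10 vs 0.05 | 0.20 vs 0.10 |
| *w* | 0.5 | 1 |
| *x* | 0.4 | 0.5 |
| Lost of 168, 10 vs 5 units | 8 vs 4 | 34 vs 17 |
| 10 units | 0.040 − 0.020/0.95 = 0.019 | 0.100 − 0 = 0.100 |
| 5 units | 0.020 − 0.010/0.975 = 0.010 | 0.050 − 0 = 0.050 |
| Shift | 0.009 | 0.050 |
| Share of 0.2 | under 5% | 25% |
| One-sided error at a true difference of 0.2 (nominal 2.5%) | about 3.4% | about 10.0% |

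The last row is 1 − Φ(1.96 − shift/SE), with SE = 0.62 × √(1/n₁ + 1/n₂) and the n's being the patients left. The 0.2 is read as mmol/L because an SD is given with it. It serves only as a yardstick, since the SAP states its margin as −20 units, which is not on this scale.

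**4. A second set of assumptions.** Suppose only the 10-unit arm loses patients (2% to 10%), with falls 0.31 to 0.62 mmol/L (0.5 to 1 SD) larger than the rest. The shift is the share lost times the extra fall: 0.02 × 0.31 = 0.006 up to 0.10 × 0.62 = 0.062. Error at a true difference of 0.2, from 160 per arm before withdrawals, is 3.1% to 13.8%.

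**5. Direction.** Both sets assume *x* > 0, which moves the result toward non-inferiority. If withdrawn patients had smaller falls, *x* is negative and the shift has the opposite sign.

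**6. Glucose.** An event at 60 minutes is recorded before any withdrawal it prompts. What can be lost is the scheduled 120-minute reading.

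**The case against.** The strongest case against is that the text permits loss but does not impose it. Withdrawal is discretionary, and Section 21 states a default of performing assessments, with a qualifier. This stands: events can remove patients, but the documents do not say that they will.

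A reader might infer that hypoglycaemia is a withdrawal trigger. The documents do not say so. It is a prespecified secondary outcome, the medication card tells the nurse to inform the doctor or research assistant, and the appendix flow chart has repeated glucose checks after an event. A reader might also infer that the hypoglycaemia endpoint is badly damaged. It is not, because a 60-minute event is already counted.

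A reader might take the violation ground to mean that results are deleted once an audit finds an error. No passage discards data already collected, and the Section 24 algorithm documents and reports violations without removing anyone from analysis. Nor does withdrawal serve only to lose data: Section 21 passes the patient to the clinician's standard care.

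Finally, it is fair to say that every input to the bias is assumed and that the moderate case is small. The introduction cites studies with more hypoglycaemia on 10 units but no difference in potassium lowering, alongside one contrary study, so the sign is open.

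What remains is that no available passage secures the 120-minute potassium once a patient is withdrawn, and the sections disagree on when a patient's study ends and who is in ITT. The withdrawal form is listed in the Protocol contents, but its text was not available for this review. If it already requires the sample, the sections need only be aligned with it.

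**Conclusion.** The point holds as a gap that allows avoidable and possibly dose-related loss of the primary outcome. It does not show that such loss will occur or that it favours 5 units.

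The possible shift is about 0.01 to 0.05 mmol/L in the two main scenarios. The upper figure needs complications in 20% and 10% of patients by 60 minutes, all withdrawn and none sampled. That would lose about 50 patients against an allowance of 16. The shift reverses if withdrawn patients had smaller falls.

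The SAP clause that drops the patient is the restriction in Statistical analysis. Withdrawal alone does not contradict an all-randomised population. Priority: should-fix, as a cheap improvement. A sample not taken at 120 minutes cannot be recovered at analysis.

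**What to change.** - **Protocol Sections 5 and 21:** separate stopping study treatment from ending data collection. Take and record the scheduled 60- and 120-minute glucose and the 120-minute laboratory potassium in every randomised patient, unless the patient refuses further data collection or valid consent is absent. Replace the conditional wording in Section 21 with this rule.
- **Protocol violations:** stop using a violation as a ground for ending data collection or leaving ITT. Log it, keep the patient in the assigned arm, and handle it in the per-protocol analysis.
- **Protocol Section 7:** align the end-of-study statement with Sections 5 and 21.
- **SAP:** reconcile the two ITT definitions and prespecify how a missing 120-minute potassium is handled, with a sensitivity analysis that is conservative for non-inferiority. State how ITT treats patients enrolled on a blood-gas value whose laboratory potassium is below 5.5, whom the inclusion footnote and the study flow chart exclude.

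Clinical care after a complication stays with the treating physician; none of this changes it.

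The cost is wording in both documents and, if needed, a line on the withdrawal form. The samples are already scheduled. The small downside is that some ITT patients will have had incomplete treatment, a deviation or additional care.
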